7.5. Criteria for early termination of the trial

The trial may be completed prematurely:

- if the trial reveals serious adverse events associated with the use of the trial drug and makes its further use unacceptable from an ethical point of view;
- when new information is received that indicates a high risk for the trial participants;
- in the case of circumstances considered as force majeure events;
- at the request of the Federal Regulatory Authorities and at the decision of the Sponsor.

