- ***Possible.*** Clinical manifestations of AE, laboratory findings deviations associated with the time of drug administration, but they can be explained by the presence of concomitant diseases or other drug administration and the influence of chemical compounds. Information on drug withdrawal response is unclear.
- ***Questionable.*** Clinical manifestations of AE, changes in laboratory findings occur in the absence of a clear temporal association with the product administration;

other factors are present (medicinal products, diseases, chemicals), which may be the cause of their occurrence.

- ***Unlikely.*** Clinical manifestations of AE, laboratory findings deviations related to UAR, are difficult to assess. Additional data are needed for assessment, or the data are currently being analyzed.
- ***Unclassified.*** Reports on suspected AE cannot be assessed, due to insufficient information, or it is contradictory.

In the case of AEs, the choice of measures (follow-up, non-drug or drug therapy, hospitalization, and/or prolongation of existing hospitalization) is made by the physician-investigator based on the patient's interests to create optimal conditions and provide the patient with needed medical care.

Patients are monitored in the center until the full completion of any AE that occurred during the trial, and in the case of the development of a chronic disease – until the condition is stabilized. AEs in the form of changes in laboratory findings are observed until the normalization of the values or until the diagnosis of the chronic disease that caused such changes.

Serious adverse event (SAE)

A serious adverse event (SAE) is defined as any adverse event (AE) that at any dose results in:

- * death and/or disability;
- * development of a life-threatening condition;
- * prolongation of existing hospitalization;
- * development of congenital anomalies or malignant tumors.

In addition, any severe bleedings will be considered as SAEs in this trial:

- major bleeding (type 3 and 5) according to BARC classification;
- hemodynamic collapse within 7 days.

AEs that do not fall into these categories should not be regarded as serious.

Any SAE, regardless of the causal relationship with the drug under trial, must be reported to the Ministry of Health of the Russian Federation no later than 24 hours after the Investigator became aware of the SAE.

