All paragraphs in the appropriate SAE report form must be filled in. Information about the SAE should be included in the CRF.

Bleedings

All bleedings should be registered in the patient's CRF. Each bleeding is classified according to BARC. Bleeding that is classified according to BARC as type 3 or 5 are considered as SAE in this trial.

Safety assessment is carried out based on the number and severity of AEs and SAEs detected during the trial.

If a serious adverse event occurs, the Investigator must:

- provide (if necessary) appropriate qualified medical care, including laboratory and instrumental studies;
- inform to the Sponsor within 24 hours about the occurrence of SAE and send (fax, e-mail) a Report form on a SAE;
- indicate all adverse events in the patient's CRF;
- continue to monitor the patient's condition until the SAE is fully completed.

In connection with SAE occurrence, the sponsor is obliged to:

- notification of administrative control authorities;
- suspend or cancel the clinical trial.

Contact information for security specialists is listed below:

Company name – Sponsor	The Russian Academy of Sciences
Legal address	[name]
Actual address	[name]
Phone [contact]
e-mail	[contact]
Authorized representative of the Sponsor	[name] [contact]

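### Section 12 obliges the sponsor to suspend or cancel the trial whenever an SAE occurs, which does not fit the discretionary grounds in Section 7.5 or a trial planned around about 31 deaths

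*Combined protocol and SAP*

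**What the plan says.** Section 12 (Safety endpoints) closes its SAE procedures with a list of sponsor duties. The stem is "In connection with SAE occurrence, the sponsor is obliged to", and two items follow: notifying the authorities, and "suspend or cancel the clinical trial". Both items share the mandatory stem and neither carries a qualifier. The list of investigator duties just above it does mark one action as needed only if necessary.

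The same section defines the events that trigger the duty. SAEs include "death and/or disability", BARC type 3 and 5 bleeding, and "hemodynamic collapse within 7 days". Causality does not limit SAE reporting: "Any SAE, regardless of the causal relationship with the drug under trial, must be reported".

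Section 7.5 (Criteria for early termination of the trial) is worded differently. "The trial may be completed prematurely" introduces a list of grounds. The SAE ground is met "if the trial reveals serious adverse events associated with the use of the trial drug and makes its further use unacceptable"; the unacceptability is an ethical judgement. The other grounds are new information showing a high risk to participants, force majeure, and a regulator's request together with a sponsor decision.

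Three other sections bear on the point. Section 11 makes all-cause death within 7 days the primary outcome. Section 17 plans 310 patients at an expected mortality of 10% in both groups. Section 19 has a committee review efficacy and safety at 25%, 50% and 75% of enrolment.

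**The concern.** One section mandates, without conditions, what another permits only on stated grounds. Take a death unrelated to study treatment. Under Section 12 it triggers a sponsor obligation to suspend or cancel. Under Section 7.5 it does not meet the SAE ground, and stopping is optional even when a ground is met.

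The mismatch matters more here than in most trials, because the triggering events are the ones the trial has to accumulate. Death is the primary endpoint, and haemodynamic collapse within 7 days is both an SAE and a secondary endpoint. A sponsor following Section 12 to the letter would suspend or cancel repeatedly for expected endpoint events. A sponsor that ignored it would depart from its own protocol at each SAE. A sponsor that applied it selectively would have no written criterion for choosing, in a trial where treatment assignment is known.

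**Working it through.** **Inputs, all from the combined protocol and SAP**

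- Expected mortality p = 10% in both groups, taken from published in-hospital mortality after alteplase of 8% to 13.4% (Section 17).
- Planned enrolment 310, as 155 per group; 141 per group before dropout; margin 10 percentage points; 80% power; one-sided 2.5% (Section 17).
- Committee reviews at 25%, 50% and 75% of enrolment (Section 19): 0.25 × 310 = 77.5, 0.50 × 310 = 155 and 0.75 × 310 = 232.5, or about 78, 155 and 233 patients.

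**Step 1. Reproduce the plan's own figure.** With p1 = p2 = 0.10 and a margin of 0.10, the Section 17 formula gives n = (1.960 + 0.842)² × [0.10 × 0.90 + 0.10 × 0.90] / 0.10² = 141.28 per group. The plan states 141; strict rounding up gives 142. For dropout, 141 × 1.10 = 155.1, against 155 stated (dividing instead, 141 / 0.9 gives 157). The sample size therefore does rest on 10% mortality, and nothing in this point changes it.

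**Step 2. Expected deaths.** 310 × 0.10 = 31. Over the cited range, 310 × 0.08 = 24.8 and 310 × 0.134 = 41.5.

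**Step 3. Position of the first patient to die, in order of enrolment.** Treating patients as independent with the same risk p:

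- mean position = 1/p
- P(no death among the first n) = (1 − p)^n
- median = smallest n with (1 − p)^n ≤ 0.5
- 95% point = smallest n with (1 − p)^n ≤ 0.05

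| Mortality | Expected deaths in 310 | Mean position | Median position | 95% probability by |
|---|---|---|---|---|
| 8% | 24.8 | 12.5 | 9 | patient 36 |
| 10% | 31 | 10 | 7 | patient 29 |
| 13.4% | 41.5 | 7.5 | 5 | patient 21 |

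At 10%, 0.9^7 = 0.478 and 0.9^30 = 0.042. The chance of reaching the first committee review without a death is 0.9^78 ≈ 0.0003; across the cited range it is 0.0015 (8%) to 0.00001 (13.4%).

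**Step 4. Set the sections side by side.**

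| | Section 12 | Section 7.5 |
|---|---|---|
| Force | obligation | permission |
| Trigger | any SAE | a listed ground |
| Relatedness needed for the SAE ground | no | yes |
| Benefit-risk judgement needed for the SAE ground | no | yes |
| Action | suspension or cancellation | premature completion |

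Bleeding and collapse SAEs would also trigger the Section 12 duty. The documents give no rates for them, so all that can be said is that the first trigger comes at or before the first death.

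**The case against.** The strongest reply is that the two sections can be obeyed together. Section 7.5 lists several grounds, and the last refers to a sponsor decision. Read as standing alone, it lets the sponsor stop whenever it chooses. Section 7.5 is also permissive and says nothing about suspension, so a sponsor that suspends after every SAE breaches nothing in it. This stands. A reader might infer that the two rules are mutually exclusive, or that Section 7.5 allows stopping only for drug-related SAEs. The text supports neither reading.

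A reader might also infer that the trial would end at about the first death and could never reach 310 patients. That does not follow either. Section 12 offers suspension as an alternative to cancellation, and a suspension can be temporary. Literal compliance means repeated interruption, not necessarily termination.

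The literal reading is also hard to square with the authors' intent. The sample size, the three committee reviews and the use of SAE counts as a safety outcome all assume that the trial continues through SAEs. The English is rough at this point, so a loosely translated list of possible sponsor actions is plausible. The documents do not confirm this, and if it is the cause, the sentence still needs correcting.

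Finally, the arithmetic mainly shows that deaths occur in a trial with a mortality endpoint. That is fair. Its use is to show that the clause would operate early and often, not in a remote contingency.

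**Conclusion.** The point holds as an inconsistency in an operative safety clause. Section 12 imposes an unconditional duty that does not match the discretionary, conditional grounds in Section 7.5. Nor does it fit the continued enrolment assumed in Sections 17 and 19. At the planned 10% mortality, the literal clause would be triggered at or before the first death (median patient 7, mean patient 10) and again at each later SAE, with about 31 deaths expected over the trial.

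These figures rest on three assumptions:

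- The 10% comes from in-hospital mortality. Deaths within 7 days may be fewer, but any death on study is an SAE whatever its timing.
- Patients are independent with equal risk.
- Positions count enrolment order. More patients may already be enrolled by the time the first death occurs.

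No endpoint, sample size or analysis is affected. The practical harm lies in conduct: repeated interruption if the clause is followed, protocol departures if it is ignored, and ad hoc decisions in an open-label trial if it is applied selectively. Correcting it is worthwhile and proportionate.

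**What to change.** Amend the protocol so that the sponsor's duty on an SAE (Section 12), the grounds for suspending or stopping the trial (Section 7.5) and the role of the committee reviews (Section 19) are stated consistently. The amended text should make clear whether the Section 12 item is an obligation or an option, and how it relates to the Section 7.5 grounds. It should also say whether it covers SAEs that are themselves efficacy endpoints. Which rule governs is for the sponsor to decide; no stopping rule is proposed here.

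The cost is about one sentence in an amendment, submitted for ethics approval as Section 4.1 already requires. Sample size, endpoints and analysis stay as they are.

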13. CASE REPORT FORM

Primary data means all the information contained in the original medical records and their certified copies, describing the results of clinical observations, examinations, and other activities, allowing to restage the trial and assess it. Primary data is included in the primary documentation (originals or certified copies thereof).

Data entered in the CRF will be confirmed by other primary documents.

For the tests performed in the central laboratory, it is necessary to attach a copy of the analysis results to the CRF.

It is necessary to attach CTPA data on CD media, ECG, EchoCG with description, and an ultrasound protocol of the inferior vena cava system to the CRF.

Erroneous records are crossed out with a single line so that it can be read. Correct records are made nearby. All records and corrections are dated and signed by the physician-investigator.

The original documents should be available for periodic review. The original CRFs are transferred to the Sponsor upon completion of the trial.

14. DRUG STORAGE AND ACCOUNTING

The study drug will be properly labelled. The label will indicate the name and dose of the drug, expiration date, storage conditions. The drug package will have an inscription: «For clinical trial use only». It is unacceptable to use the drug in patients not included in this trial.

The drug is delivered to a research center on demand and stored in a dry place at a temperature of 2-25 °C. Only Investigators have access to the drug. The packaging of the used drug must be preserved and returned to the Sponsor.

The Regulatory Authorities will require accounting for all the necessary drugs received by each research center. The following information should be entered into the register: the date of issue, date of administration, dose, and patient to whom the drug was administered. When using each dose of the drug, the corresponding record is made in the patient's medical history and in the patient's CRF (date and time, batch number of the drug, and the initials of the person who prepared the drug for administration).

The patient's number, date, and time of administration should also be indicated on the drug package.

Drug accounting will be controlled by the Monitor during visits to the research center.

At the end or termination of the trial, the form for accounting the trial product should be completed and verified; all discrepancies should be clarified, and their cause should be indicated in the documentation. According to the requirements of the Regulatory Authorities, all unused research materials must be returned to the Sponsor at the end of the trial. It is allowed to dispose of empty vials in the research center, but only after the use of the drug has been checked by the Monitor.

15. CONFIDENTIALITY

Confidentiality of a patient's personal data is protected by the current laws and legislation. The names and surnames of all patients participating in the trial are strictly confidential. Participants are identified by their initials and the individual number assigned.

The surname and other personal information will not be included in the reports and publications related to this trial. Direct access to the medical records will be available to the trial Monitor, the audit, and representatives of the control bodies when verifying the authenticity of the information obtained during the trial.

16. PARTICIPATION IN THE TRIAL AND COMPENSATION

No payments and/or compensation are provided for participation in this trial. The trial drug, medical examinations, laboratory, and instrumental studies are free of charge for all participants. The patient has the right to information about the results of medical examinations.

In accordance with Article 44 of the Federal Law No. 61 “On the Circulation of Medicines”, all patients involved in a clinical trial are subject to compulsory life and health insurance. In the case of harm to the patient's health as a result of the clinical

trial, the patient is obliged to provide the Insurer with an individual identification code for receiving the insurance premium.

17. SAMPLE SIZE CALCULATION

In the Russian Federation, multicenter randomized clinical trials of PE thrombolytic therapy have not previously been conducted. The largest clinical material of PE thrombolysis – 236 patients over 15 years – was collected in the Faculty of Surgery Clinic of N.I. Pirogov Russian National Research Medical University [1].

The calculation of the number required was carried out taking into account the capacity of 80 % and planning of a non-inferiority study in parallel groups [10]. The null hypothesis (H_0) was that the thrombolytic therapy with Fortelyzin® is inferior to the standard thrombolytic therapy with Actilyse®. This means that frequency of the primary efficacy criterion in the comparison group (P_{Actilyse}) is higher than in the group of the study drug ($P_{\text{Fortelyzin}}$) (δ):

$$H_0: P_{\text{Fortelyzin}} - P_{\text{Actilyse}} \leq -\delta$$

The alternative hypothesis (HA) is that Fortelyzin® therapy is non-inferior to the standard thrombolytic therapy with Actilyse:

$$H_A: P_{\text{Fortelyzin}} - P_{\text{Actilyse}} > -\delta$$

The calculation of the sample size for the “non-inferiority” hypothesis, the primary criterion representing the proportion of respondents, and even 1:1 distribution in therapy groups is carried out according to the following formula [11]:

$$n = \frac{(z_{1-\alpha} + z_{1-\beta})^2}{(\delta - \Delta)^2} [p_1(1 - p_1) + p_2(1 - p_2)]$$

where n – the number of patients in each of the groups compared;

p_1 – the proportion of respondents (reaching the primary efficacy criterion) in the group of the study drug;

p_2 – the proportion of respondents in the comparison group with Actilyse®;

$\Delta = p_1 - p_2$ – the expected difference between the proportions of respondents in the groups of the study drug and the comparison drug;

δ – “non-inferiority” boundary

α and β – probabilities of type I and II errors, respectively;
 $Z_{1-\alpha}$ and $Z_{1-\beta}$ – critical values of the standard normal distribution.

The limit of clinical significance was chosen to be 10% and was calculated as follows.

According to published results, hospital mortality from massive PE without treatment is 30% [12]. Since placebo control is unethical and given the characteristics of the disease (the insignificant role of the placebo effect is obvious), the absence of treatment can be considered equivalent to the placebo effect.

In-hospital mortality after thrombolysis with bolus and bolus-infusion alteplase ranges from 8% to 13,4% with an average of 10% [13, 14].

The expected mortality in both treatment groups is 10%. The clinically acceptable difference limit was chosen to ensure that at least 50% of the effect of the comparator drug relative to placebo/no treatment is retained. Thus, the difference between mortality is $(30\% - 10\%) / 2 = 10\%$. With a planned study power of 80% and a one-sided confidence interval of 2,5%, the minimum number of patients enrolled in the study is estimated to be 141 patients per treatment group to maintain 80% power for the comparison. Taking into account a possible 10% dropout rate, the sample size was increased to 310 patients to 155 patients in each group.

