11. EFFICACY ENDPOINTS

- Primary efficacy outcome – death from any causes within 7 days;
- Secondary efficacy outcome – PASP (V1, V2, V4, V5);
- Secondary efficacy outcome – hemodynamic collapse within 7 days;
- Secondary efficacy outcome – recurrent PE within 7 days;
- Secondary efficacy outcome – death from PE within 7 days;
- Secondary efficacy outcome – death from any causes within 30 days;
- Secondary efficacy outcome – clinical composite of hemodynamic collapse within 7 days + recurrent PE within 7 days + death from any causes within 30 days.

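### The non-inferiority hypotheses point the wrong way for a death endpoint: excess mortality on Fortelyzin falls in the non-inferior region

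*Combined protocol and SAP*

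**What the plan says.** Section 11 sets the primary endpoint: "Primary efficacy outcome – death from any causes within 7 days". A higher proportion is therefore worse.

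Section 17 states the null hypothesis in words as Fortelyzin being inferior to Actilyse, and then explains it: "This means that frequency of the primary efficacy criterion in the comparison group" exceeds that in the study-drug group. The formal null is "H_0: P_{\text{Fortelyzin}} - P_{\text{Actilyse}} \leq -\delta" and the alternative is "H_A: P_{\text{Fortelyzin}} - P_{\text{Actilyse}} > -\delta".

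The sample-size formula in the same section uses p1, defined as "the proportion of respondents (reaching the primary efficacy criterion) in the group of the study drug", and p2, the same proportion on Actilyse. The numbers put into it are deaths: "The expected mortality in both treatment groups is 10" (per cent). The margin is also a mortality margin, 10 points, obtained as half of the gap between 30% untreated and 10% treated mortality.

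Section 18 lists a two-sided Fisher exact test, odds ratios with 95% confidence intervals, and p below 0.05. It names no non-inferiority test, confidence limit, margin or direction.

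**The concern.** P counts deaths, but the hypotheses are written as if P counted successes. Read as printed, the region labelled inferior is the one where Fortelyzin has at least 10 points fewer deaths. Every excess of deaths, however large, lies in the region labelled non-inferior.

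The error that a non-inferiority trial with a mortality endpoint must control is accepting a drug under which more patients die. The printed hypotheses control the opposite error. Section 17 is the only place where the plan says formally what non-inferior means, and nothing in Section 18 corrects it. The trial is open-label, and Section 19 has a committee reviewing efficacy at 25%, 50% and 75% of enrolment. Choosing the direction after data have been seen would be a post-hoc change to the primary decision rule.

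**Working it through.** **Inputs (Sections 11 and 17).** P = proportion dead within 7 days; expected P_F = P_A = 10%; δ = 10 points; one-sided α = 2.5%; power 80%; 141 per arm before dropout, 155 after.

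**The plan's own sample size.** n = (1.96 + 0.84)² / 0.10² × (0.10 × 0.90 + 0.10 × 0.90) = 141.28 with unrounded normal quantiles. The plan states 141 (strict rounding up gives 142), and 141 × 1.10 = 155.1 gives its 155. The figure is reproduced. On the survival scale, 90% versus 90%, p(1 − p) is the same and so is n.

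**What the printed hypotheses mean.** With P_A = 10% and δ = 10 points, HA is P_F > 10% − 10% = 0%. Mortality of 20% or 30% on Fortelyzin therefore lies inside HA, and H0 is true only at P_F = 0%.

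**A clue in the formula.** The denominator is (δ − Δ)² with Δ = p1 − p2. For positive δ that is the squared distance from Δ to a boundary at +δ. A boundary at −δ, as in the printed H0, would need (δ + Δ)². The two agree here only because Δ = 0. The formula and the mortality-based margin point one way, and the hypotheses point the other.

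**Size of the error.** Assumed rule: conclude HA as written if the lower limit of the two-sided 95% interval for P_F − P_A exceeds −10 points. The correctly directed rule requires the upper limit to be below +10 points.

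Normal approximation, n = 141: Pr(HA as written) = Φ[(P_F − P_A + 0.10)/SE − 1.96], where SE = √{[P_F(1 − P_F) + P_A(1 − P_A)]/141}.

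- 20% vs 10%: SE = √(0.25/141) = 0.0421; Φ(0.20/0.0421 − 1.96) = Φ(2.79) = 0.997.
- 30% vs 10%: SE = √(0.30/141) = 0.0461; Φ(0.30/0.0461 − 1.96) = Φ(4.54) > 0.9999.
- 3.4% vs 13.4%: the numerator is 0; Φ(−1.96) = 0.025.

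Exact binomial enumeration with Newcombe limits, n = 141:

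| True mortality, Fortelyzin vs Actilyse | Non-inferior, as written | Non-inferior, direction corrected |
|---|---|---|
| 20% vs 10% | 99.7% | 2.6% |
| 30% vs 10% | over 99.99% | about 0.002% |
| 5% vs 10% | 33% | 99.7% |
| 3.4% vs 13.4% | 2.4% | over 99.99% |

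The 30% is the plan's untreated mortality, and 13.4% is the top of its quoted range for alteplase. Wald limits give the same picture (3.5% instead of 2.4% in the last row). At equal mortality of 10% the two rules have the same probability, 79.8% with Wald limits, so the planned power does not reveal the slip.

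**Examples at 155 per arm (Wald intervals).**

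- 31 vs 16 deaths: +9.7 points (+1.8 to +17.6). The lower limit exceeds −10, so non-inferior as written.
- 47 vs 16 deaths: +20.0 points (+11.3 to +28.7). Also non-inferior as written.
- 3 vs 16 deaths: −8.4 points (−13.6 to −3.1). The lower limit is below −10, so the null of inferiority is not rejected although Fortelyzin has significantly fewer deaths.
- Against 16 Actilyse deaths, any Fortelyzin count from 0 to 10 fails as written.

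**The case against.** The best defence is that the intent is plain. The null is correctly described in words as inferiority, the margin only makes sense as a cap on excess deaths, and the formula speaks of respondents. If P were survival, both hypotheses would be right as printed. That makes a slip from a responder template likely, but the survival reading is not in the text. Respondents are defined as patients who reach the primary criterion, which is death, and the rates used are mortality. The explanatory sentence and both formulas also err in the same direction, so this is not a stray sign.

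Three qualifications stand:

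- The confidence-limit rule behind the probabilities is assumed, and the harm depends on applying Section 17 literally. A careful analyst would probably notice.
- Failing to reject the null is not a finding of inferiority. The 3.4% versus 13.4% example uses the upper end of the alteplase range. At the planned 10% on Actilyse, a drug with 3% mortality would still pass as written about 16% of the time.
- The rest of the plan is not blind to harm. The two-sided Fisher test in Section 18 would show significantly more deaths on Fortelyzin with probability about 0.60 (141 per arm) or 0.65 (155 per arm) at 20% versus 10%, and about 0.99 at 30% versus 10%. The committee also reviews results during enrolment.

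None of this replaces a correctly directed non-inferiority test.

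**Conclusion.** The concern holds. With P as the 7-day death proportion, which is what Sections 11 and 17 say, the hypotheses are reversed and contradict the plan's own margin rationale. Applied literally, they would accept a doubling of mortality from 10% to 20% as non-inferior almost every time, where the correct rule would do so at about the nominal 2.5%. They would also usually withhold non-inferiority from a drug that halves mortality. The direction of the error follows from the text alone. The probabilities rest on literal use of Section 17, a two-sided 95% confidence-limit rule and the stated arm sizes. The sample size is not affected. This must be corrected, because it is the plan's only formal statement of its primary hypothesis.

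**What to change.** In Section 17, define P as the proportion dead from any cause by day 7 and write H0: P_F − P_A ≥ +δ against HA: P_F − P_A < +δ, with δ = 10 percentage points. Correct the explanatory sentence so that inferiority means mortality on Fortelyzin exceeding that on Actilyse by at least δ. Replace the references to respondents with the proportion dead by day 7. The printed denominator (δ − Δ)² already fits this direction.

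The alternative is to define P as 7-day survival (90% expected) throughout and keep the signs. The denominator must then become (δ + Δ)², so the first option is cleaner.

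State the same rule in Section 18: conclude non-inferiority if the upper limit of the two-sided 95% interval for P_F − P_A is below +10 points, and name the interval method. Date the change relative to any data review. The cost is text only; the sample size is unchanged because the assumed difference is zero.

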8. DESIGN AND PLAN OF RESEARCH ACTIVITIES

This trial is a multicenter, open-label, randomized, parallel-group, phase III b non-inferiority trial to compare the efficacy and safety of the trial drug.

The trial will include 310 patients with massive PE. The patients will be monitored for 30 days: 1-2 days in the Intensive Care Unit and the Department of cardiology in the remaining days before discharge (on average 14 days), with an outpatient visit on the 30th day.

Start of research, initiation of centers: «_____» 20____

Enrollment of patients: «_____» 20____

Result processing and reporting: «_____» 20____

The enrollment period may be extended to total patient enrollment if a research center fails to enroll the planned number of patients. The end date of the trial is considered to be the end date of the trial in all patients involved.

In each research center, the subject of the trial is assigned a serial number that corresponds to the sequence of patient inclusion in the trial. The serial number is reflected in the CRF. The list of patient's identification is stored in the trial file. Patients are included in the trial only after signing the Informed consent form.

Before the trial, all patients will undergo the following procedures: collection of thorough medical history, signs of hemodynamic collapse, risk stratification to assess the prognosis according to the PESI classification, a physical examination, CTPA, ECG, EchoCG with the definition of PASP, ultrasound diagnostics of the inferior vena cava will be performed; blood and urine samples will be taken for laboratory tests:

- **complete blood count:** hemoglobin, red blood cells, hematocrit, leukocyte formula: neutrophils, eosinophils, basophils, monocytes, lymphocytes, platelets, ESR;
- **biochemical blood parameters:** total protein, creatinine, urea, AST, ALT, CK, NT-proBNP, total bilirubin, glucose, sodium, potassium, total cholesterol, HDL-cholesterol, triglycerides;

- **coagulogram:** fibrinogen, aPTT, INR, prothrombin, D-dimer.
- **general urine analysis:** red blood cells.

After enrollment, patients will be randomized using the «envelope method» into two equal groups of 155 patients each (a total of 310 people, including 10% who may have dropped out) and assigned to receive either Fortelyzin® or Actilyse®. Fortelyzin® will be given as single i.v. bolus over 10-15 seconds. Actilyse® will be administered following the instruction for use.

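### The claim in Section 17 that a 10-point margin keeps at least half the alteplase effect holds only at in-hospital alteplase mortality of 10% or below, and is not tied to the 7-day primary endpoint

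*Combined protocol and SAP*

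**What the plan says.** Section 17 sets the non-inferiority margin at 10 percentage points on the absolute scale. The reason given is that, with this limit, "at least 50% of the effect of the comparator drug relative to placebo/no treatment is retained". Two inputs support it, both in-hospital figures:

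- Untreated patients: "hospital mortality from massive PE without treatment is 30" percent, a single cited value.
- Alteplase: mortality "ranges from 8% to 13,4% with an average of 10" percent.

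Half the gap between 30% and 10% gives the margin. Section 17 then uses the same 10% as the expected mortality in both arms and arrives at 141 patients per arm, raised to 155 for dropout.

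The endpoint has a different window. Section 11 lists "Primary efficacy outcome – death from any causes within 7 days". The longer window is secondary only: "Secondary efficacy outcome – death from any causes within 30 days". Section 8 plans 1 to 2 days in intensive care and then the cardiology department "in the remaining days before discharge (on average 14 days"), so the expected stay is about twice the primary window.

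The protocol gives no 7-day mortality for untreated or alteplase-treated patients, no interval around the 30% or the 10%, and no argument linking in-hospital to 7-day mortality.

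**The concern.** The trial has no untreated arm, so the margin alone connects a non-inferiority result to evidence that the new drug preserves a benefit over no treatment. Half-retention is the only justification Section 17 offers for 10 points, and it is worded as a guaranteed minimum.

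Two things undermine that wording. The guarantee is computed at one value of a quoted range, with nothing in reserve, so any higher alteplase mortality breaks it. It is also computed for deaths up to discharge and then applied to deaths up to day 7. If part of the absolute benefit accrues after day 7, the 7-day effect is smaller than 20 points and a fixed 10-point margin gives away more than half of it. A result that passes the margin would then support less than Section 17 leads a reader to expect.

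**Working it through.** **1. The plan's own figures (Section 17).**

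Margin: (30 − 10)/2 = 10.0 points.

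Sample size, from the formula in Section 17 with p₁ = p₂ = 0.10, Δ = 0, δ = 0.10, one-sided α = 0.025 and power 80%:

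n = (1.960 + 0.842)² × (0.09 + 0.09) / 0.10² = 141.28 per arm, against 141 stated. For dropout, 141 × 1.10 = 155.1, against 155 stated.

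Both reproduce. The rounding is immaterial.

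**2. Retention over the quoted alteplase range.**

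With alteplase mortality m (in %), untreated mortality fixed at 30% and a margin of 10 points, retained share = 1 − 10/(30 − m).

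| Alteplase in-hospital mortality | Effect (points) | Half the effect | Retained with a 10-point margin |
|---|---|---|---|
| 8% | 22.0 | 11.0 | 54.5% |
| 10% (average) | 20.0 | 10.0 | 50.0% |
| 13.4% | 16.6 | 8.3 | 39.8% |

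The condition 1 − 10/(30 − m) ≥ 0.5 requires m ≤ 10. At m = 13.4%, untreated mortality would have to be at least 13.4 + 20 = 33.4% for 10 points to keep half.

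**3. The 7-day window (illustration only).**

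Let f be the share of the in-hospital effect already present by day 7. The documents do not give f. At the 10% average the 7-day effect is 20f points, and retention is 1 − 10/(20f).

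| Assumed f | 7-day effect (points) | Retained with a 10-point margin |
|---|---|---|
| 1.0 | 20 | 50% |
| 0.9 | 18 | 44% |
| 0.8 | 16 | 37.5% |
| 0.7 | 14 | 29% |

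At the average rate, any f below 1 puts retention below 50%. At the favourable 8% rate the effect is 22f, so half is kept only if f ≥ 20/22, about 0.91.

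**The case against.** Several things can be said for the plan.

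- **The margin was built on the average, not the extreme.** This stands. At 8 to 10% alteplase mortality the half-retention statement is true for in-hospital death. Choosing the average over the upper end is a judgement about conservatism. What does not stand is describing the result as a minimum when it is met exactly at the average and missed above it.
- **The day-7 loss is unknown.** This also stands. A reader might infer that the trial keeps only some 29% of the effect, but that needs f = 0.7, which is an assumption. Entry requires cardiac arrest, shock or persistent hypotension, so most deaths may be early and f may be close to 1. It could exceed 1 if an early benefit were later lost. The 14-day stay describes this trial's schedule, and the observation windows of the cited sources are not stated. The gap is that f is neither given nor argued.
- **The consequence for the trial result.** A reader might infer that a marked excess of deaths would still pass. Take 14 against 8 deaths. With 155 per arm, the upper 95% limit is 9.57 points by Wald and 9.97 by Newcombe, but 10.007 by the score method, which fails. With 141 per arm, all three fail (10.5, 10.9 and 10.9). Section 18 names no interval for the risk difference, so the documents do not settle such a case. Nor do they say that a positive result will be reported as keeping half the benefit.
- **The sample size.** A reader might infer that 141 per arm is wrong. It is right for its inputs.

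**Conclusion.** The point holds in a limited form. The half-retention property claimed for the margin is not delivered by the document's own figures. It applies to in-hospital mortality only, is exactly 50% at the average alteplase rate, and ranges from 39.8% to 54.5% over the quoted 13.4% to 8%. For the 7-day primary endpoint, retention is not established in either direction, although any share of the effect below 1 by day 7 would take it under 50% at the average rate.

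These figures treat the 30% untreated mortality as fixed, because the protocol gives no interval for it. The fault lies in the wording of the guarantee and in the unbridged change of window, not in the subtraction or the sample size. The documents do not support a specific 7-day retention figure, nor a claim that the margin fails across the whole quoted range.

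**What to change.** **Section 17, wording.** Replace the guarantee with a statement to this effect: *retention is about 50% at the average alteplase rate and about 40 to 55% over the quoted alteplase range, for in-hospital mortality, with the 30% untreated rate taken as fixed; retention at 7 days is not established.*

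**Section 18, one added analysis.** Prespecify the risk difference in 30-day all-cause death with a two-sided 95% CI, read against the same 10-point margin and presented beside the 7-day result as supportive. Thirty-day death is already a secondary outcome with a day-30 visit. Thirty days covers the average stay, so it is closer to the basis of the margin than 7 days, but it is not the same as in-hospital death and the margin was not derived for it.

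One apparent shortcut should be avoided: computing retention from the observed 7-day Actilyse rate against the 30% in-hospital figure. That repeats the mismatch and flatters the result. At an observed 5%, for example, it would give 1 − 10/(30 − 5) = 60%.

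**Cost.** A less favourable stated retention and one extra analysis of data already collected. No patients are added. Guaranteeing half-retention over the whole in-hospital range would instead need a margin of at most 8.3 points. At 80% power with 10% dropout that means about 458 patients in total if mortality is 10%, or 590 if it is 13.4%. That is not asked for here, and it would still leave the 7-day question open.
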